NCT03756571

ANALYSIS PAN

Cerebral Palsy: Ankle Foot Orthoses - Footwear Combinations

August 7, 2018

Analysis Plan:

For both Specific Aims, our primary analysis will be an intent-to-treat analysis using outcomes collected during the parallel group RCT phase, (i.e., before TSAFO group crosses over to AFO-FC). This will be cross-sectional analysis based on linear regression models in which outcomes at primary endpoint of T1 (3-month) are the dependent variables, group indicator is the predictor of interest, with including baseline outcomes, and biomarkers of age, gender, gait pattern (equinus or crouch) and GMFCS. A secondary repeated measure analysis based on mixed effects models will also be conducted to examine the changes in outcomes across all 3 time points (T0, T1 and T2). In this analysis, group indicator will be entered as a time-varying predictor given the waitlist design (for AFO-FC group the indicators take values (0, 1, 1), whereas for TSAFO group the indicators take values (0, 0, 1)), time will be modelled as a discrete variable, and between group differences will be examined by group-by-time interactions and likelihood ratio test.

Study Design and Randomization.

A randomized waitlist trial [38] will be used to compare the AFO-FC to TSAFO (See Fig. 4). After enrollment, subjects are randomized to either wearing the AFO-FC (the intervention group) or TSAFO (waitlist group). There will be three main time points for assessment (T0, T1, T2) with the initial baseline assessment (T0) split over 2 visits. The first baseline visit includes consent, randomization, casting for orthoses (AFO-FC or TSAFO), and completion of parental report surveys (physical activity, function, satisfaction). For subjects in the intervention group, the second baseline visit includes attachment of accelerometer for 2 week assessment of community walking, fitting and tuning of new orthoses and shoes per AFO-FC algorithm, and gait analyses in barefoot and with AFO-FC. The intervention group return after two weeks of AFO-FC wear to check/adjust alignment using the VVGL, then wear the AFO-FC for three months before returning for their third assessment visit (T1). For subjects in the waitlist group, the second baseline visit includes fitting new TSAFO, attachment of accelerometer and gait analyses in barefoot and with TSAFO. They then wear

the new TSAFO for three months before returning for their third assessment visit (T1) after which they cross-over to the intervention group and undergo the same protocol as the original intervention group. The same outcome measures are administered at baseline and 3 months post fitting (T1) to assess effect of AFO-FC or TSAFO wear. At 6 months post fitting (T2), all outcomes except gait analyses are collected again to assess retention (T2).

To ensure internal validity of treatments and address reported parental concerns (See C.3. Aim #1), all orthoses will be cast, fit and tuned by a single study orthotist and PI. Cascade Orthotics, Bellingham, WA, USA, will fabricate all orthoses. Standardized shoes will be provided to minimize challenge of finding shoes for both TSAFO and AFO-FC. The PI and study orthotist will meet weekly to review quality of devices, fitting and tuning of all orthoses/shoes. A single orthotist will make all the orthoses, which will keep fabrication, (i.e. material thickness, trim lines), consistent. Consistency of AFO-FC prescription will be further facilitated by use of a published decision tree [8, 37] that the PI has experience (6 years) implementing within clinical practice at Seattle Children's Hospital. The local study team will meet monthly to review enrollment data, data collection logistics, and data quality (survey/gait lab/StepWatch). This information will then inform any adjustment to the protocol needed to troubleshoot challenges and ensure valid data collection and study completion. Per the decision tree and confirm internal validity of the AFO-FC intervention, a single video vector gait lab (VVGL) re-evaluation will occur 2 weeks post initial fitting to adjust and confirm that a "clinically optimal AFO-FC" was obtained. Optimal AFO-FC is defined as when thigh alignment in static standing is as close to vertical as active and passive hip and knee range of motion allow, the child can attain and maintain this posture spontaneously, and approximation of this alignment is observed during midstance of gait [39, 40] (Fig. 3).

Participant Characteristics.

We will enroll 30 ambulatory children with spastic diplegia CP, aged 4-9 years and Gross Motor Function Classification System (GMFCS) levels of II or III [41]. All participants will be clinically appropriate for a solid AFO based on physical exam/visual gait analysis criteria of: (1) insufficient gastrocnemius length to allow knee extension with ankle dorsiflexion of 10 degrees and an uncompromised foot arch; (2) low tone in the calf muscles with inability to control dorsiflexion during stance; (3) insufficient calf muscle strength to prevent excessive dorsiflexion in stance and create a 'quasi stiff' ankle in terminal stance that allows the heel to rise from the ground; and (4) insufficient triplanar boney stability of the foot during stance phase dorsiflexion [5, 6, 30]. Sample will be stratified by age (< 6 years or older) and GMFCS level. Only children with spasticity as their primary movement disorder and abnormal leg segment alignment during stance (crouch or equinus), will be enrolled to partially control for the heterogeneous clinical presentation found in this population. Elementary school age children are included, per ability to participate in the assessment sessions, yet limit fixed musculoskeletal

contractures often found in older children with CP. Participants who have undergone orthopedic or neurological surgery less than 6 months prior to enrollment or injection therapies (phenol, botulinum toxin) less than 3 months prior to enrollment will be excluded. Orthopedic and neurological surgeries as well as injection therapies are common interventions for children with CP in this age range and with these functional walking levels.

Outcomes Measures:

Aim #1: Gait Deviation Index (GDI) and gait speed (Aim 1) will be assessed at the Orthocare Innovations 3DGA laboratory in Edmonds, WA. At the baseline second visit (T0), gait analyses will be conducted in random order at self-selected walking speed both barefoot and with either a TSAFO or the fit/tuned AFO-FC. Three months post fitting, final gait data is collected (T1) in random order at self-selected walking speed barefoot and with the AFO-FC for the intervention group or TSAFO for the waitlist group. During 3DGA, skin-mounted retro-reflective markers are placed on the child to collect the 3D joint/segment motions and forces using an 8-camera Vicon MX system with two integrated AMTI force platforms. Consistent with best practices in motion analysis that ensures consistency of motion data, markers will be attached by the same experienced lab personnel according to the Plug In Gait model and post-processing of all gait lab data carried out by one individual. Outcome data for each limb will be summarized by averaging all trials for each walking condition (barefoot and/or TSAFO and/or AFO-FC) during each study visit (minimum of 3 trials per condition). A single number, the GDI, is derived from the deviation of the subjects' data from a normal kinematic profile dataset of kinematic features including pelvic tilt/obliquity/rotation, hip flexion/extension and abduction/adduction, knee flexion/extension, ankle dorsiflexion/plantarflexion and foot progression [13].

In order to explore specific joint kinematic changes (Aim 1) with the AFO-FC versus TSAFO that contribute to the overall GDI, we will also calculate the Gait Profile Score (GPS) and Gait Variable Score (GVS) from the GDI. Similar to the GDI, the Gait Profile Score (GPS) represents the pattern of deviation as a single number and is derived from the same individual joint/limb gait kinematics as GDI. The GPS is calculated on all gait features via the root mean square difference between the subject's data and the average of the normative data set [13]. GVS, also a single number, can only be derived from the GPS and consists of nine joint/limb gait variables for each side of the body (i.e. sagittal knee flexion midstance with an overall score for the pelvis [52].

AIM #2: The primary outcome of community walking activity will be captured with the ankle worn StepWatch (SW) accelerometer with balance quantified using the Pediatric Balance Scale. Parental report will capture physical activity with the Activity Scale for Kids – Performance version (ASKp), activity, fatigue and pain with selected items from the Patient-Reported Outcomes Measurement

Information System (PROMIS) and satisfaction with devices via the Orthotic and Prosthetic Users' Survey (OPUS). StepWatch (SW) – A pager sized accelerometer worn on the ankle, the SW, has one of the highest levels of accuracy for detecting steps across walking speeds from among commercially available monitors. SW daily stride levels for typical children and a large cohort with CP have been documented.

Power and Sample Size:

We will power this exploratory study based on our case series data (n=4, Fig. 5), published MCID for the Aim #1 primary outcomes of GDI and gait speed and published data for walking activity in CP [1, 45, 50]. A total sample size of 27 would allow 80% power to detect a 5 point GDI difference between groups with 97% power for a 7 point difference (MCID = 4.3 to 5.0) [45, 49] between TSAFO and AFO-FC. This sample size will have 83% power to detect a 0.10 m/sec difference in gait speed between groups with 95% power for a 0.15 difference (MCID=0.10 m/sec [50]) between conditions. A sample size of 27 has >99% power to detect a 2,000 strides/day treatment condition difference per StepWatch. This is based on the PI's cross-sectional StepWatch strides/day data from 134 youth with CP (GMFCS level II, n=84; level III, n=50; ages 2-14 years) with a mean difference between GMFCS levels of 1,630 strides (SD=2100) [1]. Therefore, we will enroll 30 participants to account for 10% attrition.

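### As coded, the secondary mixed model's group-by-time test has 0 degrees of freedom, and the time-varying indicator forces equal arm means at T0 and T2, so retention and crossover change cannot be estimated independently

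*SAP*

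**What the plan says.** The SAP's Analysis Plan makes the primary analysis a linear regression of the T1 outcome on group, with baseline outcome and other covariates. A secondary mixed model then covers T0, T1 and T2. On the group term it says: "In this analysis, group indicator will be entered as a time-varying predictor given the waitlist design". The values given are (0,1,1) for AFO-FC and (0,0,1) for TSAFO, and time is discrete. The test is described only by "between group differences will be examined by group-by-time interactions and likelihood ratio test". No fixed randomised-arm term, null model or degrees of freedom is given.

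On timing, Study Design and Randomization says that the TSAFO arm is assessed at T1, "after which they cross-over to the intervention group and undergo the same protocol as the original intervention group". At 6 months, "all outcomes except gait analyses are collected again to assess retention (T2". GDI and gait speed therefore have no T2 value, and the three-time-point model concerns the other outcomes, including StepWatch: "The primary outcome of community walking activity will be captured with the ankle worn StepWatch (SW) accelerometer" (Outcomes Measures, Aim #2).

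At T0, parent surveys belong to the first baseline visit, before any new device is fitted. StepWatch belongs to the second. For the AFO-FC arm, "the second baseline visit includes attachment of accelerometer for 2 week assessment of community walking, fitting and tuning of new orthoses and shoes"; for the waitlist arm, "the second baseline visit includes fitting new TSAFO, attachment of accelerometer and gait analyses in barefoot and with TSAFO".

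The protocol describes a single-group pre/post study with descriptive analysis and does not settle the matter.

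**The concern.** D is not randomised arm. It is 0 in both arms at T0, 1 in both arms at T2, and differs between arms only at T1. Once time is a factor, all the between-arm information in D sits at T1, so an interaction of D with time has nothing left to estimate. An analyst following the text would fit the interaction, see the columns dropped, and then have to choose the group variable, the tested term and the null model with the data in hand.

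Keeping D as a main effect also brings in two assumptions that the SAP does not state: equal arm means at T0 and at T2. The T2 assumption matters most. By then the first arm is 6 months past fitting, while the waitlist arm has worn the AFO-FC only since crossing over after T1. Whether those two states give the same mean is part of what a retention assessment should show, and this model assumes the answer.

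**Working it through.** The SAP gives no degrees of freedom or power for this model, so there is no stated figure to reproduce.

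**Inputs.** From the SAP: the coding of D and discrete time (Analysis Plan); a 2,000 strides/day difference, n = 27 and SD 2,100 (Power and Sample Size). Assumed: compound symmetry with correlation ρ = 0.3, 0.5 or 0.7; equal arms (13.5 each); complete data; SD 2,100 as the between-child SD at each time (the SAP attaches it to a comparison of GMFCS levels); and a T2 arm difference of 500 strides/day.

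**1. Aliasing.** The six arm-by-time cells:

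| Arm | Time | T1 | T2 | D | D×T1 | D×T2 | D − T2 |
|---|---|---|---|---|---|---|---|
| AFO-FC | T0 | 0 | 0 | 0 | 0 | 0 | 0 |
| AFO-FC | T1 | 1 | 0 | 1 | 1 | 0 | 1 |
| AFO-FC | T2 | 0 | 1 | 1 | 0 | 1 | 0 |
| TSAFO | T0 | 0 | 0 | 0 | 0 | 0 | 0 |
| TSAFO | T1 | 1 | 0 | 0 | 0 | 0 | 0 |
| TSAFO | T2 | 0 | 1 | 1 | 0 | 1 | 0 |

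In every row D×T2 = T2 and D×T1 = D − T2. Ranks of the fixed-effects matrix:
- time: 3
- time + D: 4
- time + D + D×time: 4
- time + arm: 4
- time + arm:T1 + arm:T2 (common T0 mean): 5
- arm × time: 6

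The interaction adds 4 − 4 = 0 df. D against time only has 4 − 3 = 1 df. These results do not depend on sample size, variance or correlation.

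**2. What time + D imposes.** Write the mean as m + g1·T1 + g2·T2 + d·D.
- AFO-FC-first means: m, m + g1 + d, m + g2 + d.
- Waitlist means: m, m + g1, m + g2 + d.
- Arm differences at T0, T1, T2: 0, d, 0.
- Retention (AFO-FC-first, T2 − T1): g2 − g1.
- Crossover change (waitlist, T2 − T1): g2 − g1 + d.

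Both changes are estimable, but crossover minus retention is fixed at d.

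**3. Size.** Under the stated assumptions, generalised least squares gives D estimate = (T1 difference) − [ρ/(1+ρ)] × (T0 difference + T2 difference). Take true means of (0, 2000, 2000) for AFO-FC-first and (0, 0, 1500) for waitlist. The D estimate is then 2000 − 500ρ/(1+ρ). The two-arm average is fitted freely at each time (1,000 at T1 and 1,750 at T2), so fitted retention is 750 − D/2 and fitted crossover change is 750 + D/2.

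| | True | ρ = 0.3 | ρ = 0.5 | ρ = 0.7 |
|---|---|---|---|---|
| D (T1 effect) | 2,000 | 1,884.6 | 1,833.3 | 1,794.1 |
| Retention | 0 | −192.3 | −166.7 | −147.1 |
| Crossover change | 1,500 | 1,692.3 | 1,666.7 | 1,647.1 |

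**4. Precision of the T1 contrast.** For arm × time the SE is 2100 × √(2/13.5) = 808.3. A common T0 mean multiplies it by √(1 − ρ²); time + D multiplies it by √(1 − 2ρ²/(1+ρ)).

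| | ρ = 0.3 | ρ = 0.5 | ρ = 0.7 |
|---|---|---|---|
| SE, arm × time | 808 | 808 | 808 |
| SE, common T0 mean | 771 | 700 | 577 |
| SE, time + D | 750 | 660 | 526 |
| RMSE, time + D, case above | 759 | 681 | 565 |

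For retention and for crossover change, RMSE is 637.5/547.7/434.5 under D and 676.3/571.5/442.7 under arm × time.

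**5. The T0 StepWatch question.** If T0 walking is recorded in the newly fitted device and the arms then differ by an assumed 500 at T0, with a true T1 difference of 2,000, the primary baseline-adjusted regression is also shifted: 2000 − 500ρ = 1,850/1,750/1,650.

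**The case against.** The best defence is that the text admits a sensible reading. The SAP uses group for the randomised arms as well, so the interaction may mean arm by time, which has 2 df. Alternatively, since D = arm×T1 + T2, D is itself a group-by-time term once time is in the model, and testing it against time only gives 1 df. Software would show the aliasing at once, so no wrong inference would pass unseen. Each of these readings works, but each needs a variable or null model that the sentence does not give, and the only group variable it defines makes the named test empty.

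The defence is right on three further points. A reader might infer that retention and crossover change cannot be estimated at all under D; step 2 shows that both can, and only their difference is constrained. A reader might infer that D gives worse estimates; in the illustrated case its RMSE is lower for the T1 effect and for both changes. And a reader might infer that the primary T1 regression is wholly untouched. That holds for the aliasing. It does not hold for T0 StepWatch, because baseline outcomes are covariates in that regression (step 5), so the T0 concern is not specific to this model. Nor do the documents establish it: the accelerometer is attached at the fitting visit, but the SAP does not say outright which device is worn during the baseline recording.

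**Conclusion.** The point stands as a specification error in a secondary analysis. As coded, the group-by-time likelihood ratio test has 0 df; this is algebra and rests on no assumption beyond taking the defined indicator as the group variable. Time + D remains fittable with a valid 1-df test, but it fixes the T0 and T2 arm means as equal, so both T1-to-T2 changes are biased if the arms differ at T2. With a 500 strides/day T2 difference, the bias is 115 to 206 on the T1 effect and 147 to 192 in absolute size on each change. Those sizes depend on the assumed correlations, compound symmetry, equal arms, complete data and the 500 itself; if the arm means are equal at T0 and T2 there is no bias. A better specification would bring a test that exists and unconstrained contrasts, not smaller error. Severity is minor to moderate: the analysis is secondary, the SAP calls the study exploratory, and the aliasing leaves the primary comparison alone.

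**What to change.** In the Analysis Plan, replace the test of D by time with fixed randomised arm (AFO-FC-first = 1, waitlist = 0) and discrete time:

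- **Outcomes measured at T0 before device fitting (parent surveys):** use a common T0 mean, time + arm:T1 + arm:T2, tested against time only (5 − 3 = 2 df).
- **Outcomes whose T0 value may be recorded in the assigned device (StepWatch):** use arm × time, tested against time + arm (6 − 4 = 2 df).

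For each outcome, report the T1 arm contrast, T2 − T1 in the AFO-FC-first arm as retention, and T2 − T1 in the waitlist arm as crossover change.

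If D is kept instead, test it against time only (1 df), delete the D-by-time test, and state that arm means are assumed equal at T0 and T2 and that crossover change minus retention is constrained to equal the D coefficient.

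Separately, state which device is worn during the T0 StepWatch recording, since the answer also bears on the baseline covariate in the primary regression.

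The cost is SAP wording only, with no new data. The statistical price of the arm-based models is a less precise T1 contrast: in the illustration, SE 771/700/577 with a common T0 mean or 808 with full arm × time, against 750/660/526 under time + D.

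### The likelihood ratio test in the secondary mixed model has no small-sample correction; run in the default way with about 27 children, its true size is roughly 6–7% rather than 5% (minor)

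*SAP*

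**What the plan says.** The SAP's Analysis Plan makes a linear regression at T1 the primary analysis. It then adds: "A secondary repeated measure analysis based on mixed effects models will also be conducted to examine the changes in outcomes across all 3 time points". In that model "group indicator will be entered as a time-varying predictor given the waitlist design", "time will be modelled as a discrete variable", and "between group differences will be examined by group-by-time interactions and likelihood ratio test".

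The SAP does not state ML or REML, the covariance or random-effects structure, the reference distribution of the test, a small-sample correction, or a significance level. The statistical section of the protocol describes only a descriptive analysis, so it does not fill these gaps.

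Power and Sample Size (SAP) gives the size of the data set: "A total sample size of 27 would allow 80% power to detect a 5 point GDI difference between groups", and "we will enroll 30 participants to account for 10% attrition". The Study Design and Randomization section of the SAP leaves gait analysis out of the T2 assessment, so GDI and gait speed have two time points and the other outcomes three.

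**The concern.** A likelihood ratio test of fixed effects compares two maximum-likelihood fits, and the usual reference is chi-square. Both are large-sample devices. ML divides residual sums of squares by the number of observations rather than by the residual degrees of freedom, so the variance is estimated too low. The chi-square reference then ignores the uncertainty in that estimate. With about 27 children neither effect is negligible, and both push p-values down.

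This is the only planned analysis that uses the T2 data, and it would be applied to several outcomes: StepWatch activity, balance, ASKp, PROMIS items and OPUS. A secondary result just under 0.05 would look a little stronger than it is. The primary regression would ordinarily be judged against t or F distributions, so the same children would face two different standards within one report.

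**Working it through.** **Inputs from the SAP.** 27 evaluable children, 30 enrolled, 10% attrition, discrete time, likelihood ratio test. The covariates "biomarkers of age, gender, gait pattern (equinus or crouch) and GMFCS" are stated for the primary model; the mixed model was tried with and without four covariates.

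**Assumptions, because the documents are silent.** Two-sided 5%; ML fits with a chi-square reference; 14/13 allocation; normal errors; no missing data; random-intercept (compound-symmetry) or unstructured covariance.

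**The plan's own figures.** 27/(1 − 0.10) = 30, as stated. For a two-group t-test with 27 children in total, 80% power at 5 GDI points implies an SD of about 4.46. That SD gives 97.5% power at 7 points, against a stated 97%. So 27 is the total for a two-group comparison, and the figures are consistent with a two-sided 5% level.

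**Exact size.** For balanced complete data without covariates, the likelihood ratio statistic is a fixed function of the usual t or F statistic. The chi-square cut-off can therefore be converted to a t or F cut-off and its true tail read off. The cut-offs are 3.841 (1 df) and 5.991 (2 df).

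1. *Two visits, group-by-time, 1 df.* LRT = n·ln(1 + t²/(n−2)). It rejects when |t| > √(25 × (exp(3.841/27) − 1)) = √(25 × 0.1529) = 1.955. The correct cut-off on 25 df is 2.060. True size **6.2%**.
2. *Three visits, random intercept, 2 df.* LRT = 2n·ln(1 + F/(n−2)). It rejects when F > 25 × (exp(5.991/54) − 1) = 25 × 0.1173 = 2.934. The correct F(2,50) cut-off is 3.183. True size **6.2%**.
3. *Three visits, unstructured, 2 df.* LRT = n·ln(1 + 2F/(n−3)). It rejects when F > 12 × (exp(5.991/27) − 1) = 12 × 0.2485 = 2.981. The correct F(2,24) cut-off is 3.403. True size **7.0%**.

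With all 30 children the three sizes are 6.1%, 6.1% and 6.7%.

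**Simulation under the null.** This covered two and three visits, within-child correlation 0.3 and 0.7, with and without four covariates, and both readings of the group term: the 1-df time-varying indicator and the group-by-time interaction. There were 20,000 runs per random-intercept setting (standard error about 0.2 percentage points) and 6,000 per unstructured setting (about 0.3).

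| Rejection rate at nominal 5% | Random intercept | Unstructured |
|---|---|---|
| n=27 | 5.6–7.4% | 5.9–8.1% |
| n=30 (two visits with covariates not run) | 5.8–6.5% | 6.1–7.6% |

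The rates near 8% at n=27 are for the time-varying indicator with unstructured covariance. With covariates it gives 7.9% at three visits for either correlation, and 7.5–8.1% at two visits.

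**Check of the remedy.** Using finite-sample references at n=27, without the four covariates, simulated rejection was 4.9–5.1% with F(2,50) under a random intercept, 5.1–5.2% with F(2,24) under unstructured covariance, and 4.8–5.2% with t(24) for the T1 contrast adjusted for T0. These are the finite-sample F and t references themselves; Kenward-Roger software was not run.

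**The case against.** The strongest reply has four parts.

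- *The SAP does not call the test asymptotic.* This stands. The chi-square reference and the 5% level are assumptions. They are the usual default, and an analyst following the sentence as written would most likely apply them, but the conclusion must be conditional on that.
- *The model is not settled.* This also stands. The time-varying indicator, with values (0,1,1) and (0,0,1), differs between arms only at T1, so it carries 1 df. A 2-df interaction over three visits needs a fixed arm variable that the SAP does not define. That is a separate matter to resolve. It does not remove this point, because the rejection rate exceeded 5% under both readings and both covariance structures.
- *The consequence is small.* This stands and sets the severity. The excess is about 1 to 3 percentage points in an analysis labelled secondary, within a study labelled exploratory. No sample size or power figure rests on it.
- *Kenward-Roger is a preference.* This stands in part. Other small-sample methods would serve, but the SAP names none.

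A reader might go further and infer an error rate near 10%. Simulated rates of 7.3–9.7% do occur, but for a joint 3-df test of all group terms with covariates, which the SAP does not specify. A reader might also infer that reported confidence intervals will be too narrow. The SAP plans no ML-based intervals, and an analyst could test by ML and report REML intervals.

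**Conclusion.** The point holds in conditional form and is minor. The SAP names a test that, run with ML fits and a chi-square reference at an assumed two-sided 5%, rejects a true null in roughly 6–7% of trials of about 27 children. It can reach about 8% with unstructured covariance plus covariates; 6% is not a strict floor, since one simulated setting gave 5.6%. The upper end depends on a covariance structure that the SAP does not name. For GDI and gait speed, with two visits, the exact unadjusted figure is 6.2%. The sizes rest on normal errors and complete data.

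It would be wrong to infer that the trial's main comparison is compromised: the primary T1 regression is a separate analysis that does not use this test.

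**What to change.** In the Analysis Plan of the SAP, change the sentence on the mixed model so that it is fitted by REML and fixed-effect contrasts are tested by F or t tests with a small-sample degrees-of-freedom method (for example Kenward-Roger), with matching confidence intervals. Alternatively, keep the likelihood ratio test and state that its p-value comes from a parametric bootstrap or permutation reference. The same edit should state the covariance structure, the significance level and the group term being tested.

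The cost is one or two sentences and slightly larger p-values in the secondary analysis. Data collection, sample size and the primary analysis do not change.

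### The only T0 StepWatch recording described appears to be made in the randomised device, yet the SAP adjusts for it as a baseline and codes the AFO-FC arm as unexposed at T0

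*SAP*

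**What the plan says.** SAP, Study Design and Randomization, splits T0 over two visits. On the first it says: "The first baseline visit includes consent, randomization, casting for orthoses (AFO-FC or TSAFO), and completion of parental report surveys (physical activity, function, satisfaction"). No accelerometer is listed there. For the AFO-FC arm the second visit includes "attachment of accelerometer for 2 week assessment of community walking, fitting and tuning of new orthoses and shoes per AFO-FC algorithm". For the waitlist arm, "the second baseline visit includes fitting new TSAFO, attachment of accelerometer and gait analyses in barefoot and with TSAFO". Then: "The intervention group return after two weeks of AFO-FC wear to check/adjust alignment using the VVGL". The same section adds that "a single video vector gait lab (VVGL) re-evaluation will occur 2 weeks post initial fitting to adjust and confirm" the result.

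SAP, Analysis Plan, sets the primary model for both aims: "outcomes at primary endpoint of T1 (3-month) are the dependent variables, group indicator is the predictor of interest, with including baseline outcomes", plus age, gender, gait pattern and GMFCS. For the secondary mixed model the group indicator varies with time: "for AFO-FC group the indicators take values (0, 1, 1), whereas for TSAFO group the indicators take values (0, 0, 1"). It continues: "time will be modelled as a discrete variable, and between group differences will be examined by group-by-time interactions and likelihood ratio test".

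SAP, Outcomes Measures, AIM #2, makes StepWatch community walking the primary outcome of that aim.

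**The concern.** Adjusting for a baseline is safe when treatment cannot have affected it. Here the baseline StepWatch value comes after randomisation and apparently after the device is on. Any device difference already present in those two weeks is carried into the covariate, and the regression removes part of the treatment effect along with it. The mixed model has the same fault: it treats the AFO-FC arm's T0 value as unexposed.

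The Aim 2 primary estimate then rests on an unstated assumption that AFO-FC and TSAFO do not differ in their effect on walking during the first fortnight. If that fails, the bias can go either way. A pre-device StepWatch value that was never recorded cannot be recovered in the analysis.

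The surveys listed for the first visit are not affected, because they precede fitting.

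**Working it through.** **Visit order.** In both arms, attachment and fitting fall at one visit. In the AFO-FC arm the recording lasts two weeks and the child returns after two weeks in the AFO-FC, so the recording and wear windows coincide. No other T0 StepWatch recording is described. The Protocol (Study Design) does take its baseline in current orthoses, but it describes a 10-child single-arm pre/post study and does not settle the randomised design.

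**The plan's own power figure.** SAP, Power and Sample Size, gives n = 27, a difference of 2,000 strides/day, SD 2,100 and power above 99%. Alpha is not stated; two-sided 5% is assumed.
- Paired comparison of 27 children, taking 2,100 as the SD of the difference: 99.9% (normal) or 99.7% (t). This matches.
- Parallel groups of 13 and 14: about 70% (normal) or 66% (t). This does not match. Baseline adjustment would bring it to 99% only with a T0–T1 correlation of about 0.82 or more, which the SAP does not state.

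**Primary regression.** Let d1 be the 3-month difference and d0 the difference during the T0 recording. The adjusted estimate has expectation d1 − slope × d0 = d1 × (1 − slope × share), with share = d0/d1. For example, 2,000 × (1 − 0.5 × 0.25) = 1,750 and 2,000 × (1 − 0.7 × 0.5) = 1,300.

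Power was simulated (100,000 trials, 13 and 14 per arm, planned covariates included). SD 2,100 is taken as the total SD. The GMFCS difference of 1,630 with 50 of 134 at level III accounts for (50/134)(84/134) × 1,630² / 2,100² = 14% of the variance, leaving a within-level SD of 1,946. Slope, share and the true effect of 2,000 are assumptions.

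| Early share | Slope 0.5: estimate, power | Slope 0.7: estimate, power |
|---|---|---|
| 0 (as with a true pre-device baseline) | 2,000, 76% | 2,000, 90% |
| 25% | 1,750, 64% | 1,650, 75% |
| 50% | 1,500, 49% | 1,300, 53% |
| −20% | 2,200, 83% | 2,280, 95% |
| T0 not in the model | 2,000, 66% | 2,000, 66% |

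Independent repeats gave the same estimates within simulation error, with power up to three points lower.

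With no effect at either time the test keeps its 5% level. With no 3-month effect but an early loss of 500 strides/day, the expected estimate is 0.5 × 500 = +250 or 0.7 × 500 = +350, and the simulated type I error is 6.3% or 8.5%.

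**Mixed model, indicator as coded, discrete time, exchangeable correlation r.** The between-arm differences at T0, T1, T2 are (share × d, d, 0), and the coding says (0, 1, 0). Generalised least squares gives d × [1 − share × r/(1 + r)]. For r from 0.3 to 0.9:
- 25% share: 1,885 down to 1,763
- 50% share: 1,769 down to 1,526

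If group in the interaction sentence instead means the randomised arm, the T0-to-T1 contrast is d × (1 − share): 1,500 at 25% and 1,000 at 50%.

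**The case against.** The strongest reply is that the premise is inferred. No sentence names the device worn during the T0 recording, and the design figure is not visible. The authors call T0 a baseline, code both arms 0 there, and list the accelerometer before fitting in the AFO-FC arm. This limits certainty, but it does not supply another reading: item order within one visit cannot move a two-week recording ahead of it, and in the TSAFO arm fitting is listed first. Calling T0 unexposed is the step in question, not evidence for it.

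Second, the early effect may be small, and the study is described as exploratory. Both points stand. The check that may adjust the AFO-FC comes two weeks after fitting, so a full early effect is not assumed here, and the early loss of 500 is only an illustration. The documents give no basis for assuming zero either.

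Third, the power figures depend on the reading of the SD. This also stands. If 2,100 is the within-level SD, power is about 59% without T0, 69% or 84% with a true baseline, and 43% or 46% at a 50% share (slope 0.5 or 0.7). The biases do not change.

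Fourth, with the indicator as defined, multiplying it by discrete time adds nothing estimable, so the randomised-arm version is not the stated coding. That is fair. It leaves the smaller mixed-model losses as the main figures, and the interaction sentence needs clarifying.

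**Conclusion.** The concern holds. As written, the SAP adjusts the Aim 2 primary outcome for a value recorded after randomisation and, on the natural reading of the visit schedule, during wear of the allocated device. It also codes that time as unexposed. The direction of the bias follows from the sign of the early effect relative to the 3-month effect: toward no difference if they agree, away from it if they are opposite, none if there is no early effect.

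The size cannot be fixed from the documents. With a quarter to a half of a 2,000 strides/day effect present early and slopes of 0.5 to 0.7, the primary estimate loses 250 to 700 strides/day. This rests on the assumed slope and share and on the visit reading above; confidence is moderate because the SAP never names the device worn. The point needs correcting before analysis, since it concerns a primary estimate and the main repair is a change of wording.

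**What to change.** 1. **Primary StepWatch regression.** Remove the post-fitting T0 value from the covariates, keep age, gender, gait pattern and GMFCS, and report T0 StepWatch as an early post-fitting outcome. Alternatively, start the T0 recording at the casting visit, before the new device is worn; this is still after randomisation but before exposure. If the recording is already meant to precede device wear, state that, and the covariate and the 0 code can stay.
2. **Mixed model.** State whether group means the time-varying indicator or the randomised arm. If T0 StepWatch stays post-fitting, add a separate term for AFO-FC at T0, and state that the model then assumes equal arms at T2, although the original AFO-FC arm has worn the device longer. The unadjusted T1 comparison in (1) does not need that assumption.
3. **Lesser clarification, gait.** SAP, Outcomes Measures, Aim #1, measures GDI and speed barefoot and in the device at both T0 and T1 without naming the baseline or the endpoint. Name barefoot T0 as baseline and with-device T1 as endpoint.

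**Cost.** The first option in (1), and items (2) and (3), are SAP wording with no new data. Dropping T0 gives about 66% power, against 76% or 90% with a true pre-device baseline. It also has less power than the planned covariate when the early share is below about 21% (slope 0.5) or 36% (slope 0.7); what it buys is freedom from this bias. The casting-visit option needs at least two weeks between casting and fitting, an interval the SAP does not state, and a way to return the monitor. The T0 term multiplies the mixed-model standard error by (1 + r)/√(1 + 2r), about 3% to 14% more for r from 0.3 to 0.9. If the original AFO-FC arm keeps a T2 advantage of 20% of the effect, that model recovers 1 − 0.2r, or 0.94 to 0.82 of it; with a 20% deficit, 1.06 to 1.18. A barefoot gait baseline may correlate less with with-device T1.
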